2 STUDY OBJECTIVES

To compare the effectiveness of the iEHR + Navigator versus usual care control, we propose a 2-arm RCT with a stratified cluster randomization of child primary care practices with 4 practices each randomized to iEHR + Navigator or usual care control arms.

2.1 Primary Objective

Parental combusted tobacco quit rate at 1 year, as assessed by validated surveys, biochemically-confirmed at 12-months compared between iEHR + Navigator vs. usual care control.

Hypothesis. Parental 7-day combusted tobacco quit rates, as assessed by validated surveys, biochemically-confirmed at 12-months, will be greater for iEHR + Navigator vs. usual care control (outcome for which study is powered).

2.2 Secondary Objectives.

The secondary objectives are to:

[figure not shown]
1. To compare parents' self-reported adoption of tobacco free behaviors (quit attempts, use of pharmacotherapy, use of Quitlines and institution of smoking and vaping bans in their homes and cars) between the iEHR + Navigator & usual care arms
2. To establish the incremental cost per quit of the iEHR + Navigator vs. usual care arms
3. To assess the implementation and sustainability of the intervention in the iEHR + Navigator arm (NRT prescription and Quitline referrals as assessed by the parental report around 12-months, the screening survey conducted at check-in, and EHR

documentation of screening and services delivery fidelity, before and immediately following implementation, 6, 12, 18, 24, 30, and 36 months).

3 INVESTIGATIONAL PLAN

3.1 General Schema of Study Design

This is a stratified cluster randomized controlled trial of minimum 8 child primary care practices with minimum 4 practices each randomized to iEHR + Navigator or usual care control arms:

¹Practices will be randomized to 2 arms, with 4 sites in each arm and ~400 parent subjects per arm (~100 per site). Approximately 800 parent subjects across 8 sites (~100 per site) will be enrolled. Enrolled parents will be followed up at approximately 12 months (could be sooner or later depending on the visit schedule/parent availability).

²Parent screening and enrollment procedures may be modified to kiosk/telephone/remote screening and enrollment due to procedures that may be in place at CHOP to protect people from COVID-19 risks.

3.1.2 Parent Screening & Enrollment

Control and intervention practices will be trained in integrating Research Assistants (RAs) who will be hired, trained, and paid by the research study for data collection. A notice may be posted at the practice entrance/registration window/waiting room of participating practices, informing parents accompanying their children to office visits that the practice is participating in the research study (posting details may be modified based on practice layout and preferences). We will deploy several in-person (at CHOP pediatric primary care) and remote (via e-mail, phone and/or text) strategies for screening and enrolling smoking parents to maximize recruitment efforts.

The study team will review patient medical records and those parents who identified themselves as smokers, will be approached by RAs and offered enrollment in the longitudinal cohort. We will continue to enroll parents until approximately 100 parents have been enrolled in the longitudinal cohort in that practice. Parent screening and enrollment procedures may be modified to kiosk/telephone/remote screening and enrollment due to procedures that may be in place at CHOP to protect people from COVID-19 risks.

The detailed description of the screening and enrollment procedures is under *section 4.1 Screening & Enrollment*.

3.1.3 Intervention

The intervention consists of an innovative EHR platform, iEHR, which will be used to screen families for tobacco use and refer smoking parents to smoking cessation resources and treatment. Components of the iEHR will include automated EHR-generated NRT prescription, automated enrollment in the free Quitline and/or SmokefreeTXT program, and a brief motivational message delivered by the clinician (as prompted by the EHR). As an added service, it may also include a referral to the company called BrightMedical that will facilitate the delivery of the NRT medication to interested families. Community Health Navigator support will be offered to all smokers enrolled in the intervention arm. CHNs will provide customized smoking cessation support to household tobacco users through phone follow-up and/or home visits, depending on the needs of each family and as study resources allow.

See a detailed description of the iEHR + Navigator intervention and its components under *section 4.2.1*.

3.1.4 Follow-Up

Enrolled parents will be followed-up with a survey after approximately 12-months. Those parents who do not return at annual check-up will be contacted remotely (e.g., phone, text, HIPPA-compliant video system, email, portal (myCHOP) messaging). Parents who self-report 7-day abstinence at the 12-month surveys (in-person or by phone/text) will be asked to submit their saliva for cotinine testing. In addition to the cotinine test, for parents who report current use of NRT or e-cigarettes or have a cotinine level of $\geq 10\text{ng/ml}$, the readings from the carbon monoxide levels test will also be used to confirm self-reported smoking cessation.

See a detailed description of the follow-up procedures under *section 4.3 Follow-Up*.

3.2 Practice Selection, Randomization and Blinding

At least eight CHOP practice sites will be approached and selected by PeRC network leadership.

All practices are eligible to participate. We will preferentially enroll practices with the following criteria:

1. A minimum 10% Medicaid insurance rates for children
2. An average patient flow of 40 families per day
3. A willingness to have a Research Assistant in the office setting

Eligible practices will be randomized to: (1) 'iEHR + Navigator' and (2) 'usual care control' arms (4 practices in each arm). Practices will be matched based on practice size (based on the number of children seen in a typical year (this will account for COVID-19)) and the Medicaid rate at the practice.

In this 2-arm cluster randomization of practices to 'iEHR +Navigator' and 'usual care control' arms (4 each), we will recruit four matched pairs of practices through the CHOP network. Practices will be matched with respect to size and Medicaid rate. Within each of these pairs of practices, we will assign one to the intervention and the other to control, using computer generated random allocation. When the four assignments are complete, a fifth computer-generated random number will assign either "A" or "B" to the intervention. The statisticians will be blinded as to which of "A" and "B" is the intervention until the analyses are completed. In the event that a practice drops out, we will replace it with the most similar practice based on practice size and Medicaid rate from the pool of unassigned and interested practices. In the event the enrollment is slower than projected, we will add additional practices from the CHOP network, with practices matched in pairs based on practice size and Medicaid rate, from the pool of unassigned and interested practices. We will randomly allocate these practices in pairs to the control and intervention arms, as needed and in decreasing order of projected enrollment rate.

A practice leader will be identified in each practice. This person will be the study team's contact person at the practice.

At the end of data collection, all control practices will be offered the iEHR intervention.

3.3 Study Duration, Enrollment and Number of Sites

3.3.1 Duration of Study Participation

Each parent participation will last 12 months.

Each clinician and staff participation in the intervention practices will last 36 months. Clinician and staff participation and study activities are described in detail under section *4.3.3 Practice Clinicians and Staff Qualitative Interviews*.

Practice data will be collected for approximately 36 months post implementation.

The sections below will focus on the parents' participants.

3.3.2 Total Number of Study Sites/Total Number of Subjects Projected

The study will be conducted at a minimum of 8 primary care sites at CHOP with approximately 40 clinicians participating across these 8 sites, and proportionally more clinicians if other sites are added.

Our goal is to stop recruitment when 400 parent subjects are enrolled per arm in the longitudinal cohort (800 across both arms). The study has been designed to achieve this goal by recruiting 100 parents from each of four sites per arm, and for this situation we will have 80% power for the primary outcome (iEHR + Navigator vs. usual care control), for a clinically meaningful difference in smoking cessation rates. If some practices accrue subjects at a rate which makes it unlikely that these practices can achieve the recruitment goal of 100 subjects, then we will estimate the likely shortfall, and increase the recruitment goals in faster-accruing practices in order to attempt to preserve statistical power. We may also add additional practices to maximize the likelihood of meeting the recruitment goal of at least 400 parents enrolled in each arm. If we add practices, we will do so in pairs, matched by practice size and Medicaid rate, and randomly assigned to the control and intervention groups. If the study must be terminated before the recruitment goal, this termination will be made exclusively for reasons (such as time and budget) which are unrelated to study outcomes.

In the intervention practices, a minimum of one clinician and one key staff will complete an in-depth qualitative interviews 6-weeks following implementation and after 12, and 24 months.

3.4 Study Population

3.4.1 Inclusion Criteria

We will enroll parents or legal guardians who smoke, are present at the visit, and whose child is seen by a clinician in the study practice. "Smoker" will be defined as answering "yes" to either of the screening questions: "*Have you smoked a cigarette, even a puff, in the past 7 days?*" and "*Have you smoked any other tobacco product (cigars like black and mild, hookah), even a puff, in the past 7 days?*" on the iEHR pre-visit screening

questionnaire (Appendix 5 for intervention practices and Appendix 5A for control practices). The eligibility criteria will be confirmed using Eligibility Form (Appendix 10) prior to consent and enrollment. Parents will also be screened for JUUL/E-cig use. Each eligible parent who indicates cigarette and/or other tobacco product use in the past 7 days will be allowed to enroll in the study, regardless of whether or not the parent uses any type of e-cigarette or vaping device.

3.4.2 Exclusion Criteria

- 1) Parent/legal guardian does not speak English; 2) No telephone; and 3) Prior enrollment in the study during a previous visit.

Subjects that do not meet all of the enrollment criteria may not be enrolled.

Over the course of the study, parents who screened positive for smoking on the iEHR pre-visit screening questionnaire, are prompted to complete it every 3 months if they have a visit. Additionally, parents with multiple children, are prompted to complete the iEHR pre-visit screening questionnaire for each child. As a result, parents may show up as eligible for the study in the EHR multiple times despite being already enrolled in the study. We have implemented several safeguard mechanisms to avoid duplicate enrollments of such parents (checking the reports of already enrolled parents, asking parents whether they have already been enrolled in the study). Nevertheless, it is difficult to completely avoid duplicate enrollments, especially when a parent chooses not to disclose that they are already taking part in the study. The study team will monitor the REDCap projects regularly to identify any incidents of duplicate enrollment. If a duplicate enrollment is identified, the study team will notify the parent that they can be enrolled in the study only once and their information will be kept only under the original enrollment. The study team and the investigator will keep track of the duplicate enrollments to ensure validity of the data, and only use the data from the initial enrollment. This study is minimal risk, and the second enrollment does not disqualify a parent from being kept in the study under the original enrollment.

Any other violations of these exclusion criteria must be reported in accordance with IRB Policies and Procedures.

4 STUDY PROCEDURES

4.1 Screening & Enrollment

The protocol for the recruitment, consent, and retention of participants will be identical in all practices. As part of the clinical workflow, all parents in control and intervention practices will be asked about their individual smoking status on the iEHR pre-visit screening questionnaire (Appendix 5 for intervention practices and Appendix 5A for control practices). We will deploy several strategies to maximize screening and enrollment efforts.

The study team/CHOP Clinical Reporting Unit (CRU) and/or Research Enhancement Core (REC) will generate rosters of potentially eligible parents for the upcoming visit. Rosters will include all upcoming visits at study practices of parents who answered, “yes” to either of the screening questions: *“Have you smoked a cigarette, even a puff, in the past 7 days?” and “Have you smoked any other tobacco product (cigars like black and mild, hookah), even a puff, in the past 7 days?”* on the iEHR pre-visit screening questionnaire. The study team will offer enrollment into the study to these potentially eligible parents in-person at the primary care site, via the phone or e-mail.

Additionally, at participating CHOP primary care sites, study team will also review the medical records to identify parents who self-reported as smokers (answered “yes” to either of the screening questions: *“Have you smoked a cigarette, even a puff, in the past 7 days?” and “Have you smoked any other tobacco product (cigars like black and mild, hookah), even a puff, in the past 7 days?”* on the iEHR pre-visit screening questionnaire. (Appendix 5 for intervention practices and Appendix 5A for control practices) to approach them and offer enrollment in the study longitudinal cohort. If a parent is not interested in participating in the study, the research team will document this information in REDCap (child’s name, MRN, parent’s relationship to the child, practice name and date of the visit).

Potentially eligible families who are missed in the CHOP primary care sites will also be reached via recruitment emails, text messages and calls facilitated by the study team and/or CHOP Research Enhancement Core (REC). All outreach methods (e-mail, texts, calls) will include information about how parents can opt out from being contacted about this study in the future.

Smoking parents will be recruited in one of these ways:

- 1. In-office enrollment:** At participating CHOP primary care sites, study team will approach eligible parents i.e. those who self-reported as smokers (answered “yes” to either of the screening questions: *“Have you smoked a cigarette, even a puff, in the past 7 days?” and “Have you smoked any other tobacco product (cigars like black and mild, hookah), even a puff, in the past 7 days?”* on the iEHR pre-visit screening questionnaire (Appendix 5 for intervention practices and Appendix 5A for control practices) to approach them and offer enrollment in the study longitudinal cohort. Study team will confirm eligibility criteria using Eligibility Form (Appendix 10) prior to consent and enrollment. If a parent agrees, they will be consented using Informed Consent of Parent (Appendix 3b and 3bE (for intervention group) and 3 and 3E (for control group)). After consent, parents in the intervention arm will also be offered the additional support of CHOP CHNs (Attachment 11) (see section 4.2.2. Community Health Navigators for more detail). Parent Enrollment Survey (Appendix 4) will be then administered by the RA in both intervention and control

practices. The Parent Enrollment Survey (Appendix 4) includes additional questions assessing parental vaping status, stage of readiness to change, demographic information, tobacco related attitudes and behaviors and parents' contact information (~ 15 minutes).

In-office enrollment for parents that don't complete the iEHR pre-visit screening questionnaire: At participating CHOP primary care practices, screening questionnaires are assigned to a patient record as opposed to each parent and that sometimes results only in one parent being screened for smoking as opposed to each parent. The study team will fill these gaps by offering enrollment into the study for every smoking parent or legal guardian present at the visit.

2. **Hybrid enrollment from in-office to remote:** If during the office visit, the parent who was screened positive for smoking and eligible for the study (answered "yes" to either of the screening questions: *"Have you smoked a cigarette, even a puff, in the past 7 days?" and "Have you smoked any other tobacco product (cigars like black and mild, hookah), even a puff, in the past 7 days?"* on the iEHR pre-visit screening questionnaire (Appendix 5 for intervention practices and Appendix 5A for control practices) doesn't have time to complete enrollment or prefers to complete enrollment at home, the study team will ask the parent if he/she is interested in remote enrollment and will ask to collect their contact information for remote enrollment.

Hybrid enrollment if consented in office: If the eligible participant's consent was completed during the visit but the participant doesn't have time to complete the enrollment survey, we will follow up with them remotely to complete the survey or complete the survey during a future visit to the participating office.

All contact information will be stored and shared in a secure HIPAA compliant way (i.e., using CHOP OneDrive). The study team will then attempt to follow up with the parent(s) and conduct enrollment remotely.

3. **Remote enrollment:** We will also deploy additional recruitment approaches, including calling, emailing and texting eligible participants (those who answered "yes" to either of the screening questions: *"Have you smoked a cigarette, even a puff, in the past 7 days?" and "Have you smoked any other tobacco product (cigars like black and mild, hookah), even a puff, in the past 7 days?"*) on the iEHR pre-visit screening questionnaire at the study practices. The roster of eligible participants will

be generated by the study team and/or CHOP REC. Parents that were already enrolled in the study will be excluded.

For outreach calls, the study team will briefly explain the purpose of the call and introduce the study prior to consent. If the parent agrees to participate, the consent and survey will be sent to them electronically via text or e-mail. During the phone outreach, parents will not be texted or e-mailed the study materials without verbally agreeing to it during the call. All outreach emails and texts will contain the REDCap link inviting them to consider participation in the study. Parents who choose to participate will be screened for eligibility via the REDCap survey (Eligibility Form - Appendix 10) and they will provide informed consent/HIPAA authorization electronically (Appendix 3bE (for intervention group) and 3E (for control group). After they electronically sign the consent, parents in the intervention arm will also be offered the additional support of CHOP CHNs (Attachment 11) (see section 4. 2.2. Community Health Navigators for more detail). Then parents in both intervention and control groups can complete the enrollment form (Appendix 4) either at home themselves or while having a research assistant on the call. If the parent picks up the call but it's not a good a time for them to complete the enrollment, the RA may offer them an option to receive follow up with the RA via text to set up the best time for the enrollment call. The research presents minimal risk to participants and involves no procedures for which written consent is normally required outside of the research context.

If the parent has a working e-mail address on record, we may also attempt to outreach to them via e-mail (e-mail template: Appendix 12 for intervention and Appendix 13 for control). E-mail letters may be customized for each practice based on the input from practice physicians and staff. E-mail letters will include an option to opt-out from further communication and will notify the parents that if they do not enroll into the study or opt out, within 2 weeks we may follow up with them via phone call or text. Follow up texts (with up to 3 reminders if the parent doesn't opt out) will include a brief information about RAs call back number to learn more about the study. Parents may opt out at any time.

Using the workflows outlined above, we will continue to enroll parents until approximately 400 parents have been enrolled in each arm. If some practices accrue subjects at a rate which makes it unlikely that these practices can achieve the recruitment goal of 100 subjects, then we will estimate the likely shortfall, and increase the recruitment goals in faster-accruing practices in order to attempt to preserve statistical power. We may also add additional practices in one or both arms to meet the recruitment goal of 400 parents enrolled in each arm. A notice to parents

may be posted where all can see it when entering/registering for their pediatric visit. The notice may announce that the practice is participating in a research study and that parents/guardians may be approached by a study RA during their office visit. Parent screening and enrollment procedures may be modified to kiosk/telephone/remote screening and enrollment due to procedures that may be in place at CHOP to protect people from COVID-19 risks.

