screening survey conducted at check-in, and EHR documentation of screening and services delivery fidelity, before and immediately following implementation, 6, 12, 18, 24, 30, and 36 months).	
Test Article(s)	iEHR + Navigator
Study Design	2-arm Randomized Control Trial with a stratified cluster randomization
Subject Population	Inclusion Criteria
Inclusion and Exclusion Criteria:	Parents or legal guardians who smoke, are present at the visit, and whose child is seen by a child healthcare clinician in a participating practice. “Smoker” will be defined as answering “yes” to either of the screening questions: “Have you smoked a cigarette, even a puff, in the past 7 days?” and “Have you smoked any other tobacco product (cigars like black and mild, hookah), even a puff, in the past 7 days?” Dual users of e-cigarette or vaping device will also be included. Eligibility will be confirmed using the Eligibility Form.
	Exclusion Criteria
	
 1. Parent/legal guardian does not speak English; 2. No telephone; and 3. Prior enrollment in the study during a previous visit.
Number of Subjects	
Total Number of parent subjects: Approximately 800
 
Total number of clinicians and staff: Approximately 40
 
Total Number at CHOP: Approximately 840
 
Total Number of Sites: Minimum 8

Study Duration	
Each parent participation will last 12 months
 
Each clinician and staff participation in the intervention practices will last 36 months
 
The entire study is expected to last 5 years

Study Phases	
1. Practice Selection & Randomization	At least 8 CHOP practice sites will be approached and selected by PeRC network leadership and randomized to: (1) ‘iEHR +Navigator’ and (2) ‘usual care control’ arms (4 practices in each arm). In the event that a practice drops out, we will replace it with the most similar practice based on practice size and Medicaid rate from the pool of unassigned and interested practices. In the event the enrollment is slower than projected, we will add new practices that are similar based on practice size and Medicaid rate in each arm.

[figure not shown]

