9 STUDY ADMINISTRATION

9.1 Treatment Assignment Methods

9.1.1 Randomization

In this 2-arm cluster randomization of practices to 'iEHR +Navigator' and 'usual care control' arms, we will recruit at least four matched pairs of practices through the CHOP network. Practices will be matched with respect to size and Medicaid rate. Within each of these pairs of practices, we will assign one to the intervention and the other to control, using computer generated random allocation. When the four assignments are complete, a fifth computer-generated random number will assign either "A" or "B" to the intervention. The statisticians will be blinded as to which of "A" and "B" is the intervention until the analyses are completed. In the event that a practice drops out, we will replace it with the most similar practice based on practice size and Medicaid rate from the pool of unassigned and interested practices. In the event the enrollment is slower than projected, we will add additional practices from the CHOP network, with practices matched in pairs based on practice size and Medicaid rate, from the pool of unassigned and interested practices. We will randomly allocate these practices in pairs to the control and intervention arms, as needed and in decreasing order of projected enrollment rate.

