9.1.2 Blinding

The practices in each pair (the four initial pairs, and any subsequent pairs added in the event of slow accrual) will be randomly assigned labels "A" and "B". The intervention will be blinded in a separate randomization with either the label "A" or the label "B", and the other label will be assigned to the control practice. The statisticians will be blinded as to which of "A" and "B" is the intervention until the analyses are completed.

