practices accrue subjects at a rate which makes it unlikely that these practices can achieve the recruitment goal of approximately 100 subjects, then we will estimate the likely shortfall, and increase the recruitment goals in faster-accruing practices in order to attempt to preserve statistical power. If enrollment is slower than projected in some practices, we will add new practices that are similar to each other based on practice size and Medicaid rate in each arm to reach the goal of 400 parents in each arm.

A notice may be posted at the practice entrance/registration window/waiting room of participating practices, informing parents accompanying their children to office visits that the practice is participating in the research study (posting details may be modified based on practice layout and preferences). Recruitment procedures will be identical across both arms.

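### Section 4.1 lets practices be added to a single arm, which the matched-pair randomisation rule in 3.2, 3.3.2 and 9.1.1 does not allow

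*Protocol*

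**What the plan says.** Section 4.1 (Screening & Enrollment) deals with slow recruitment in two steps. For a slow practice, the team will "increase the recruitment goals in faster-accruing practices in order to attempt to preserve statistical power". It then goes on: "We may also add additional practices in one or both arms to meet the recruitment goal of 400 parents enrolled in each arm". Pairing, matching and random allocation are not mentioned there.

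Four other sections describe how practices are added:

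- Section 3.3.2 has the same goal-raising step and the same permission to add practices, but follows them with a condition: "we will do so in pairs, matched by practice size and Medicaid rate, and randomly assigned to the control and intervention groups".
- Sections 3.2 and 9.1.1 both say of practices added for slow enrolment: "We will randomly allocate these practices in pairs to the control and intervention arms". Both also say that, within a pair, one practice goes to intervention and the other to control.
- Section 9.1.2 assigns the blinded labels A and B within pairs, and describes these as "the four initial pairs, and any subsequent pairs added in the event of slow accrual".

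Two summary texts are looser. The synopsis, under practice selection and randomisation, says "we will add new practices that are similar based on practice size and Medicaid rate in each arm". Section 9.5 says "we will add new practices that are similar to each other based on practice size and Medicaid rate in each arm". Neither mentions the random step.

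**The concern.** The protocol gives two different rules for the same event, a recruitment shortfall. Under 3.2, 3.3.2 and 9.1.1, chance decides which arm a new practice joins, and each new practice has a matched partner in the other arm. Under 4.1, a practice may join one arm alone so that this arm reaches its target. Its arm is then set by which arm is short, and it has no partner.

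This matters because so few units are randomised: a minimum of four practices per arm. Random assignment of practices is the main protection against differences between them, such as patient mix, staffing and existing cessation support. A practice placed by choice falls outside that protection. The SAP plans a model adjusting for confounders that are unbalanced between arms. That reaches only measured factors, and the SAP limits it to what the sample can support.

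Section 4.1 is also where staff would look: 3.1.2 and 9.5 both send the reader there for the detailed enrolment procedures.

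**Working it through.** The plan gives no figure on this point to reproduce. The check is a comparison of rules.

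**Step 1. What the pair rule can produce.** The trial starts with at least four practices per arm. Each added pair puts one practice in each arm (3.2, 9.1.1). Starting from four and four, adding k pairs gives 4 + k intervention and 4 + k control practices: 5 and 5, then 6 and 6, and so on. Additions under this rule always keep the arms equal in number of practices.

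**Step 2. What 4.1 can produce.**

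- Adding to both arms can give 5 and 5, which is compatible with the pair rule although 4.1 does not state that rule.
- Adding to one arm gives 5 and 4, or 4 and 5. No value of k gives either result.

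The conflict is therefore confined to the one-arm option, and there it is complete.

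**Step 3. Whether random allocation could survive under the one-arm option.** The stated purpose is to bring each arm to 400 parents. If one arm is short and a practice is added to that arm alone, the shortfall has fixed the arm. Even if the practice were drawn at random from the pool, its arm would not be random. The labelling in 9.1.2 also has no step for an unpaired practice.

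**Step 4. Scale.** One practice added to a four-practice arm is 1 of 5 in that arm. The documents give no expected shortfall, so I assume a gap of s parents, filled entirely by the added practice, in an arm that reaches 400. The share of the arm outside randomisation is s / 400:

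| Assumed gap s | Share of the arm |
|---|---|
| 40 | 40 / 400 = 10% |
| 70 | 70 / 400 = 17.5% |
| 100 | 100 / 400 = 25% |

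These shares show how much of an arm could be involved. They are not estimates of bias.

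**The case against.** The best defence is that 4.1 is a permissive sentence in a recruitment section. It sets no allocation procedure and does not disclaim randomisation. Allocation is governed by the dedicated sections, where 3.2, 3.3.2 and 9.1.1 agree on matched, randomised pairs and 9.1.2 assumes pairs. On that view this is one loose phrase set against four consistent sections.

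Much of this stands. The intended rule is clear, and harm follows only if someone acts on 4.1 instead of the other sections. But the phrase names a single arm as an option, and I find no statement of which section prevails. The words in 3.2 and 9.1.1 that allow additions as required govern how many pairs are added and in what order. They do not admit an unpaired practice.

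Four stronger readings are tempting, and the documents do not support them:

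- *That a non-randomised addition is planned or has happened.* Nothing shows this. Section 4.1 permits it and goes no further.
- *That the synopsis and 9.5 are also in conflict.* Both speak of similar practices in each arm, which fits the pair rule. They leave out the random step but do not contradict it.
- *That the drop-out rule is a second route around randomisation.* Section 9.1.1 says: "In the event that a practice drops out, we will replace it with the most similar practice". This covers drop-out, not accrual. Its natural reading is that the replacement takes the vacated place. How the replacement's arm is set is left unstated, which is a missing detail and not a contradiction.
- *That the bias would favour a particular arm, or that the point is about power.* The documents do not let one predict a direction, and the objection concerns allocation alone.

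**Conclusion.** The contradiction is real, but narrow. The one-arm option in 4.1 cannot be reconciled with 3.2, 3.3.2 and 9.1.1, and 9.1.2 makes no provision for it. If used, it would put a practice with no random allocation and no matched partner into an arm of about five practices. On the assumed gaps, that practice would hold 10% to 25% of the arm's parents. The direction and size of any bias are unknown.

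The textual conflict depends on no numerical assumption. The shares depend on the assumed gap, on one added practice filling it, and on the arm reaching 400. The text should be corrected, but the finding is not evidence that the trial's allocation has been compromised.

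**What to change.** In section 4.1, replace the wording that allows addition to a single arm with the rule in 3.3.2: if practices are added, "we will do so in pairs, matched by practice size and Medicaid rate, and randomly assigned to the control and intervention groups".

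If any practice has already been added to one arm without random allocation, report it and add a sensitivity analysis of the primary outcome excluding that practice's parents. The primary analysis stays as planned.

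The correction changes wording only. It removes the option of adding a practice to the slower arm alone, but 3.2, 3.3.2 and 9.1.1 already exclude that. If only one arm is slow, the pair rule means opening an extra site in the other arm as well. The alternative is the existing rule in 3.3.2 and 4.1 of raising the goals of faster-recruiting practices. The sensitivity analysis, if needed, would be less precise because it uses fewer parents.

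Two clarifications are optional and are not part of the error: stating the random step in the synopsis and 9.5, and stating how the arm of a drop-out replacement is set.
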